1. RESEARCH QUESTIONS

1.1. OVERVIEW OF RESEARCH QUESTIONS

The primary overall research questions for this descriptive evaluation, which will be assessed utilizing pre- and post-surveys from nFORM, focus on program services and seeks to understand, "Is Strong Fathers, Stronger Families program participation associated with better participant outcomes?" This overall line of inquiry is operationalized by focusing on specific short-term outcomes to determine if parenting, co-parenting, and economic stability outcomes are improved after program participation.

No	Research Question	Implementation or Outcome?
11	Are participants offered primary workshops and support services as intended (fidelity)?	Implementation
12	How many primary workshops do participants attend (dosage), and how does this vary by workshop characteristics (e.g., timing and length of sessions) and participant characteristics (e.g., age, employment status, relationship status)?	Implementation
R1	Do SFSF-Midsouth participants experience significant increases in Co-parenting Relationship outcomes after program participation?	Primary Outcome
R2	Do SFSF-Midsouth participants experience significant increases in Parenting Relationship outcomes after program participation?	Primary Outcome
R3	Do SFSF-Midsouth participants experience significant increases in economic stability outcomes after program participation?	Primary Outcome

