9. DATA COLLECTION

9.1. CONSTRUCTS AND MEASURES

Clearly articulate the constructs of interest, measures to evaluate those constructs, and specific data collection instruments. Provide any information on the reliability and validity of the data collection instruments. For standardized instruments, you may provide the citation for the instrument.

^{*} you may add rows by hitting the tab button, or right click and select insert row below

Construct	Measure	Instrument	Reliability and Validity (if standardized instrument, you provide a citation for the instrument)
Program fidelity	Percent of enrolled participants who received each of the following: 1) primary workshops, 2) employment supports, 3) substantive service contacts, 4) referrals Number of substantive service contacts and referrals per participant	nFORM MIS	
Dosage	Number of primary workshop hours received, percent of target hours received Subgroup exploratory analysis of how dosage varies by workshop and participant characteristics	nFORM MIS	

Co-parenting Relationships	Composite measure that takes the average of 5 survey items related to positive co-parenting interactions with the mother of participant's youngest child (continuous, scale from 1-5 where 1 is strongly disagree and 5 is strongly agree). Improvement will be measured by a participant's change score, calculated by subtracting their pre-program composite score from their post-program composite score.	nFORM Community-Based Fathers Survey (A13: d-h)	Reliability and validity will be assessed with a correlation matrix and factor analysis
Parenting Relationships	Daily hours spent with youngest child in past 30 days (change score from preprogram to post-program) Frequency of reaching out to youngest child in past 30 days (change score from preprogram to post-program) Composite measure that takes the average of 10-11 survey items related to positive parenting behaviors with youngest child (continuous, scale from 1-5 where 1 is Never, 2 is 1 to 2 days per month, 3 is 3 or 4 days per month, 4 is 2 or 3 days per week, and 5 is every day or almost every day). Improvement will be measured by a participant's change score, calculated by subtracting their pre-program composite score from their post-program composite score.	nFORM Community-Based Fathers Survey (A2b, A2c, A5a-d: a-k)	Reliability and validity will be assessed with a correlation matrix and factor analysis

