Economic Stability	Difficulty paying bills (categorical, scale from 1 to 4 where 1 is never and 4 is very often). Improvement will be measured by change score in participant's reported difficulty, calculated by subtracting their	nFORM Community-Based Fathers Survey B4, B3, B3a.	N/A (individual items will not be combined)

post-program value from their pre-program value.	
Has savings account at end of program, among those who came into the program with no savings account	
Has checking account at end of program, among those who came into the program with no checking account	

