Strong Fathers, Stronger Families Healthy Marriage and Responsible Fatherhood Program Evaluation

Statistical Analysis Plan

Clinicaltrials.gov ID: NCT06907719

8/2/2023

1. Data Analysis

Briefly describe the planned approach for data analysis. If an impact analysis is proposed, name the key dependent and independent variables, and describe any methods to minimize Type I error (i.e., finding positive impacts by chance) such as limiting the number of impacts to be analyzed and/or multiple comparison correction. Describe proposed approach(es) for addressing missing data.

Identify study sample

The study sample includes participants who: 1) gave recorded informed consent to be part of the study, and 2) took both an entrance and exit survey. The CONSORT diagram in Appendix B shows exclusion criteria and the anticipated size of the overall study sample. The analytic sample for particular outcome measures will vary based on missing data.

Defining analysis measures

For each outcome construct, we have identified the relevant measures from nFORM that are theoretically aligned with that construct. We will generate a correlation matrix between items in a given construct to ensure that theoretically related items are also empirically related in our data set. Items that are not strongly correlated with other items in a construct will be removed as necessary. Factor analysis will be used to ensure that all construct items hang together (using an alpha of 0.7 or higher as the threshold).

Once we are confident that all of the items align with a given construct, we will create a composite measure by taking an average of the scores on each non-missing item in the construct. The measure definition matrix below provides information on each proposed outcome. For composite measures, a change score will be calculated between a participant's pre-program composite score and post-program composite score. For standalone survey items, a change score will be calculated between a participant's pre-survey and post-survey responses.

For the sake of consistency and simplicity, parenting and co-parenting analyses will use a participant's youngest child as the focal child.

	Sample		Data	Variable	
Measure		Variable Type	source(s)	Name	Definition
Co-	Has at least one child	Continuous	nFORM	Copar_Beh	Average of five
parenting	age 24 or younger	(range from 1 to 5	entrance,		survey items that
relationship			nFORM		relate to positive
behaviors			exit		interactions with

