		and 5 is strongly			the mother of
		agree)			participant's
					youngest child

	saw child within past month	(range from 1 to 5 where 1 is never			Average of 10 to 11 survey items (depending on child age) that relate to frequency of positive interactions with participant's youngest child
•	Has at least one child age 24 or younger, saw child within past month	(range from 1 to 24)	nFORM entrance, nFORM exit		Reported number of hours per day (excluding sleeping) that parent usually spent with their youngest child
Frequency of contact		(range from 1 to 4 where 1 is every	entrance, nFORM exit		Reported frequency of reaching out to youngest child in the past month
Economic stability – checking account	•	(0/1)	nFORM entrance, nFORM exit	_	Binary measure of having opened a checking account by the end of the program
Economic stability – savings account	_	(0/1)	nFORM entrance, nFORM exit	0 _	Binary measure of having opened a savings account by the end of the program
Economic stability – difficulty paying bills		(range from 1 to 4 where 1 is never		_	Reported frequency of difficulty paying bills

Handling missing data

Outcomes

When creating the composite measures for co-parenting and parenting relationships, we will create a composite score by taking the average of multiple individual items. For these measures, our current plan is to use 20% as a threshold for allowable missing items, based on guidance from evaluation technical assistance resources. This plan is contingent on the final distribution of missing data in our data set. With a 20% threshold, if a respondent is missing more than 1 item used for creating the coparenting construct or more than 2 items for creating the parenting construct, the respondent will be assigned a missing value for that construct. We will not be imputing truly missing values for outcomes. To create a construct score, the average will divide by the number of non-missing values in the construct.

Participants who have not seen their child within the past month will have their parenting behavior responses set to "Never" (1) and will be included in the analytic sample for that outcome.

For outcomes that use single survey items, participants who do not respond to the item on either the pre- or post-survey will be excluded from the analytic sample for that outcome.

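### Does coding contact frequency with 1 as the most frequent category make an improvement under R2 count as a decline?

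*SAP*

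**What the plan says.** The SAP's measure definition matrix (Section 1, Data Analysis) describes the contact item as "Reported frequency of reaching out to youngest child in the past month" and codes it "range from 1 to 4 where 1 is every". The readable text stops there, so the upper anchor and anything else in that cell cannot be seen.

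On the change score, Protocol Section 9.1 lists "Frequency of reaching out to youngest child in past 30 days (change score from preprogram to post-program". The SAP's general rule for single items is "For standalone survey items, a change score will be calculated between a participant's pre-survey and post-survey responses". Neither sentence gives an order of subtraction or a recode.

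Two neighbouring measures in Protocol Section 9.1 are more explicit:

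- The parenting composite uses a 1 to 5 scale "where 1 is Never, 2 is 1 to 2 days per month", so higher is better. Its change is "calculated by subtracting their pre-program composite score from their post-program composite score", that is, post minus pre.
- Difficulty paying bills runs from 1 (never) to 4 (very often), so higher is worse. Its change subtracts the "post-program value from their pre-program value", that is, pre minus post.

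The research question in Protocol Section 1.1 reads "Do SFSF-Midsouth participants experience significant increases in Parenting Relationship outcomes after program participation". The R2 hypothesis in Protocol Section 4 is that these outcomes will be better after the program.

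**The concern.** A frequency scale whose first category begins with the word every puts the most contact at the low end. The parenting composite and daily hours, the other two R2 measures, are scales on which more is better. The natural reading of a change from pre to post is post minus pre, and on the raw code that makes more contact negative. The authors did reverse the subtraction for the bills item, so its absence here looks like an oversight.

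R2 is a primary, confirmatory question worded in terms of increases. Read literally, a significant increase in the raw code would mean that fathers reach out less. A real gain could then be tabled as a worsening beside two measures that run the other way. A further worry is the SAP's correlation check, which allows poorly correlated items to be dropped. An unreversed item would correlate negatively with the rest.

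**Working it through.** **Inputs.** The code runs from 1 to 4 with 1 at the frequent end (SAP matrix, as far as it can be read). The test is a paired t-test on the change (SAP, Analytic approach). Neither document states whether the test is one-sided or two-sided. The plan gives no figure of its own to reproduce for this item.

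**One father.** Three scoring rules can be compared:

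| Pre | Post | Raw post - pre | Pre - post | Reversed: (5 - post) - (5 - pre) |
|---|---|---|---|---|
| 3 | 2 | -1 | +1 | +1 |
| 4 | 1 | -3 | +3 | +3 |
| 2 | 3 | +1 | -1 | -1 |

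The last two columns always agree, because (5 - post) - (5 - pre) = pre - post = -(post - pre).

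**The test.** Write d for the raw post minus pre change. Reversal replaces every d by -d. The mean becomes -mean(d) and the standard deviation is unchanged. The statistic t = mean(d) / (SD(d) / √n) therefore becomes -t. The two-sided p-value depends only on |t|, so it does not move. A multiplicity adjustment built from those p-values does not move either.

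A simulated example shows this. It uses 200 pairs with an assumed distribution of responses, not trial data. The raw code gives t = -0.88 and the reversed code t = +0.88, with two-sided p = 0.379 both times. Only a one-sided test for an increase differs: p = 0.81 unreversed and 0.19 reversed.

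**Can the sign contaminate another estimate?** In both documents contact frequency is a measure of its own, separate from the parenting composite. That composite averages 10 to 11 items. Protocol Section 9.1 gives their survey letters as a to k, which is 11 letters, and cites the two single items under other numbers. The contact response is therefore not averaged with items coded the other way.

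**The correlation check.** The SAP's criterion for removal is the lack of a strong correlation. A reverse-coded item can correlate strongly with a negative sign, and the sign alone does not meet that criterion. The check is a step towards building composites, and this item is scored by itself. If it is included in the matrix for the parenting row, a negative correlation would show its direction to the analyst.

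**The case for a change.** The strongest counter-argument is that the plan shows its authors know such items need a stated direction: they wrote one for the bills item and not for this one. The protocol entry for contact frequency is intact and contains no reversal, so the loss of text in the SAP table does not explain the gap. An analyst who carried over the post minus pre rule from the composites would get a negative number for an improvement. If the direction were settled only after results were seen, a confirmatory reading would rest on a later choice. An unreversed item would also lower alpha if it entered the reliability check.

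Part of this stands. The readable text gives no sign convention for the item, and one sentence would have supplied it. The rest is weaker. The post minus pre order is written for the composites, not for this item. Daily hours has the same bare wording, so the silence is not peculiar to contact frequency. The direction of benefit is not open to choice after the fact, because the hypothesis is better parenting outcomes and reaching out more often is plainly the better direction. A one-sided test would require the analyst to name a direction, and that hypothesis names it. The alpha point matters only if the single item is treated as part of a scale, which neither document proposes.

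**Conclusion.** The concern does not call for a change. The readable text supports only a narrow point: the contact item appears to be coded opposite to the parenting composite, and its scoring direction is not written down. The effect is limited to the sign of one of the three R2 measures. It does not alter the size of the change, |t|, the two-sided p-value or any other estimate. Analysts fill this kind of gap sensibly once they have the response categories in front of them, and writing the convention down would not change a sound conclusion.

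This rests on four assumptions: that 1 is the most frequent category, as the truncated cell suggests; that the t-test is two-sided, or one-sided in the direction of improvement; that the item is analysed alone, as both documents list it; and that whoever reports the result reads the sign against the category labels.

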Population: The SFSF-Midsouth Program proposes to serve low-income fathers who face barriers to engagement with their children. These participants will be primarily young fathers, including biological, expectant, and adoptive fathers, stepfathers, and acknowledged father figures. Recruitment will focus on at-risk young fathers, low-income fathers, and active-duty military and veteran fathers living in Shelby County, TN, Tipton County, TN, and Crittenden County, AR. Specific numbers to be served are in the chart below:

PROGRAM PARTICIPATION TARGETS

Milestone	Year 1 4/1/21- 9/29/21	Year 2 9/30/21- 9/29/22	Year 3 9/30/22- 9/29/23	Year 4 9/30/23- 9/29/24	Year 5 9/30/24- 9/29/25	Total
Individuals Screened	225	450	450	450	450	2,025
Participants Enrolled	175	350	350	350	350	1,575
Participants who attend at least one primary workshop	175	350	350	350	350	1,575

Participants who attend at least 50% of primary workshops	165	330	330	330	330	1,485
Participants Graduating Healthy Relationship & Parenting Curricula (attend at least 90% of primary workshops)	158 (90%)	315 (90%)	315 (90%)	315 (90%)	315 (90%)	1,418
Participants who attend 100% of primary workshops	118	236	236	236	236	1062
Participants Placed in Jobs	105(60%)	210 (60%)	210 (60%)	210 (60%)	210 (60%)	945
Job Retention- 30 days	87 (50%)	175 (50%)	175 (50%)	175 (50%)	175 (50%)	787
Job Retention- 60 days	70 (40%)	140 (40%)	140 (40%)	140 (40%)	140 (40%)	630
Job Retention- 90 days	50	100	100	100	100	450
Job Retention- 180 days	40	80	80	80	80	360
Return Post-Graduation for Long-Term Case Management	87	175	175	175	175	787

Memorandum of changes to the Evaluation Study.

- SEEDCO Midsouth will aim to serve the same number of individuals in the descriptive study as in the RCT with a different estimated minimum effect size for the descriptive study. (Evaluation enrollment targets remain unchanged)
- The one-year local evaluation follow-up survey will no longer be collected and has been removed from the evaluation plan.
- The previously administered OLLE pre- and post-surveys will not be administered, as the measures needed to answer R1, R2, and R3 come from nFORM.

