4. HYPOTHESES

For each specified research question, state the hypothesized result(s) and briefly describe why these results are anticipated.

Research Question	Hypothesized Result
I1	Primary workshops, support services, and case management services were offered to all participants as needed, with fidelity to the program model.
12	Participants received primary workshop hours (dosage) as intended, with 90% of enrollees receiving at least 90% of primary hours.
R1	Participants will experience better co-parenting relationships outcomes after program participation.
R2	Participants will experience better parenting relationships outcomes after program participation.
R3	Participants will experience better economic stability outcomes after program participation.

^{*} you may add rows by hitting the tab button, or right click and select insert row below

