9.2. METHODS OF DATA COLLECTION

If the evaluation will collect multiple waves of data, describe the timing of these waves below. When describing follow-up periods, specify whether the follow-up period will be post-baseline, post-random assignment, or post-program completion.

Wave of Data Collection	Timing of Data Collection
(e.g., baseline, short-term follow-up, long-term follow-up)	
Pre-Test (Wave 1)	Collected immediately following informed consent and study enrollment – during orientation session or first workshop

	Collected after the completion of core curriculum/primary workshop programing – during the last workshop session – approximately 8 weeks after enrollment/baseline
--	--

For each measure, describe how data will be collected detailing which data collection measures will be collected by which persons, and at what point in the programming or at what follow-up point.

Measure	Timing of Data Collection (baseline, wave of data collection)	Method of Data Collection	Who Is Responsible for Data Collection?	Impact Evaluations Only: Will Methods or Collection Procedures Differ by Study Group?	Administrative Data Only: Will data access require data sharing agreement?
nFORM Entrance Survey	Wave 1	Participant self-enters survey using online data collection platform	Data Manager will proctor data collection and assist participants as necessary		N/A
nFORM Exit Survey	Wave 2	Participant self-enters survey using online data collection platform	Data Manager will proctor data collection and assist participants as necessary		N/A

^{*} you may add rows by hitting the tab button, or right click and select insert row below

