Missing data for the implementation outcomes could happen as a result of programmatic data entry issues. For the sake of this evaluation, we assume that any primary or support services received by a participant are being accurately logged into nFORM, so a lack of documented attendance, service contacts, referrals, etc. is indicative of lack of services (i.e., a participant not receiving the program components as intended).

...

Assessing non-response bias

We will conduct response rate analysis for each primary outcome of interest to assess non-response bias and adjust for threats to internal validity. Using data from the Applicant Characteristics Survey, we will look at demographics (race, ethnicity, age, education level) and primary reason for joining the program among participants who fall into each of the following categories: 1) non-respondents who answered no surveys after the ACS, 2) respondents who completed the pre-survey only, 3) respondents who completed the post-survey only, and 4) respondents who completed both the pre-and post-survey (complete case).

Analytic approach

The main goal of this descriptive study is to assess pre-post change scores in the outcomes listed above among program participants before and after primary workshops. We will use paired sample t-tests to assess the magnitude and significance of changes among program participants in the analytic sample for each outcome. For binary economic stability outcomes, we will descriptively report the percent of participants who opened a checking or savings account during the course of the

program. We will adjust our p-values for multiple hypothesis testing and report the adjusted p-values in the appendix of the final report.

For the implementation analysis, program fidelity will be descriptively reported by the percentage of enrolled participants who receive: 1) any primary workshops, 2) employment supports, 3) substantive service contacts, 4) referrals. The program aims to provide all participants each of these four program components, so the percentage of participants who receive each of these will be compared to the 100% benchmark. Number of substantive service contacts per participant will also be compared to the benchmark of 8 SSCs set by OFA for FIRE grantees.

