Dosage will be measured by percent of target primary workshops participants attend on average (using 90% as a benchmark), and categories of attendance (initial, halfway, 90%, 100%) will be reported and compared to targets established by the program and reported on page 3 above. Exploratory analysis will examine how dosage varies by workshop characteristics (e.g., timing and length of sessions) and participant characteristics (e.g., age, employment status, relationship status)?

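### Sessions with no attendance record are scored as missed although the SAP allows for data-entry gaps, so measured dosage can read low; the exit survey offers a cheap, one-session check on the size of that error.

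*SAP*

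**What the plan says.** SAP section 1, in the missing-data text on implementation outcomes, opens with an admission: "Missing data for the implementation outcomes could happen as a result of programmatic data entry issues". The next sentence sets the problem aside: "we assume that any primary or support services received by a participant are being accurately logged into nFORM". It concludes, "so a lack of documented attendance, service contacts, referrals, etc. is indicative of lack of services". No logging-error rate and no sensitivity analysis is given.

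Dosage is then judged in three ways:

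- SAP, analytic approach: the mean percent of target workshops attended, against 90%.
- The same paragraph: "categories of attendance (initial, halfway, 90%, 100%) will be reported and compared to targets established by the program".
- Protocol section 4, the I2 hypothesis: "with 90% of enrollees receiving at least 90% of primary hours".

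Protocol section 9.1 names nFORM as the only source for dosage. Section 11.1 says that both participants and staff (facilitators, case managers) enter data there. Section 9.2 has the participant enter the exit survey himself, proctored by the Data Manager, "during the last workshop session". The entrance survey may be taken at orientation or at the first workshop. Section 11.2 lists the nFORM client ID for linking.

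**The concern.** The SAP names a source of missing data and then codes every gap as zero service. For sessions that were attended, the resulting error has one direction: an omitted entry can only lower dosage. The cut-offs are high, so one or two lost entries can move a father out of the 100% category or below 90%. A program that met its attendance targets could be reported as missing them for clerical reasons.

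The exploratory part of I2 is also exposed. If completeness of logging differs between workshops, a comparison of dosage by workshop characteristics partly compares record-keeping.

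The plan already generates a second record for one session. A father who took the exit survey in the last session was there by the plan's own procedure. If his attendance at that session was not logged, the rule still scores him absent, and no described step compares the two records.

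**Working it through.** **Inputs from the documents.** The participation targets in Protocol section 1: 1,575 enrolled, 1,418 at or above 90% of workshops, 1,062 at 100%. The mean benchmark of 90% is in the SAP.

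**Assumed, because the documents do not give them.** Loss rate e = 1%, 2% or 5%, independent across sessions; K = 10, 16 or 20 equal sessions; true attendance exactly at target.

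**Step 1. Reproduce the targets.** 0.90 × 175 = 157.5, entered as 158; 0.90 × 350 = 315; 158 + 4 × 315 = 1,418, and 1,418/1,575 = 90.0%. For full attendance, 118 + 4 × 236 = 1,062, or 67.4%. The difference, 1,418 − 1,062 = 356 (22.6%), attends 90% or more but not all.

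**Step 2. Mean percent attended.** Recorded mean = true mean × (1 − e), whatever K is. From a true 90%:

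- e = 1%: 0.90 × 0.99 = 89.1%
- e = 2%: 0.90 × 0.98 = 88.2%
- e = 5%: 0.90 × 0.95 = 85.5%

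**Step 3. Categories, K = 20.** The 90% cut-off is 18 recorded sessions. Split the 356 evenly between 18 and 19 sessions attended. The probability of at least 18 recorded is a binomial tail:

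| e | attended 20 | attended 19 | attended 18 |
|---|---|---|---|
| 1% | 0.999 | 0.985 | 0.835 |
| 2% | 0.993 | 0.945 | 0.695 |
| 5% | 0.925 | 0.755 | 0.397 |

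Share recorded at or above 90% = 0.674 × (first) + 0.226 × (second + third)/2. At e = 5%: 0.674 × 0.925 + 0.226 × 0.576 = 75.4%. At 1% and 2% it is 87.9% and 85.5%. The true value is 90.0%.

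Share recorded at 100% = 0.674 × (1 − e)^20 = 55.2%, 45.0% and 24.2%. The true value is 67.4%.

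**Step 4. Other session counts.** Place all 356 exactly at the cut-off (worst case: 9 of 10, 15 of 16 or 18 of 20):

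| e | at or above 90%, K = 10 / 16 / 20 (true 1,418) | at 100%, K = 10 / 16 / 20 (true 1,062) |
|---|---|---|
| 1% | 1,383 / 1,357 / 1,358 | 960 / 904 / 869 |
| 2% | 1,342 / 1,283 / 1,302 | 868 / 769 / 709 |
| 5% | 1,195 / 1,026 / 1,123 | 636 / 467 / 381 |

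The direction and rough size do not depend on choosing 20 sessions.

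**Step 5. What the survey match recovers.** Upper bound: the last session is restored for everyone. With the step 3 model at e = 5%, the share at or above 90% rises from 75.4% to 76.4%, and the share at 100% from 24.2% to 25.4%. At e = 1%, 87.9% becomes 88.0%. The mean becomes 0.90 × [1 − e(1 − 1/(0.9K))]. At e = 5% that is 86.0% for K = 10 and 85.75% for K = 20, against 85.5% uncorrected.

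**Step 6. I1, any primary workshop.** A father who attended K sessions drops out only if all K entries are lost, with probability e^K. For K = 10 and e = 5% this is about 1 in 10^13.

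**The case against.** **The assumption is disclosed and there is general oversight.** Protocol sections 6 and 9.3 describe a bi-weekly review of nFORM data to find and mitigate data issues, with front-line staff on the team, and training for staff and the Data Manager. This stands as context and may catch some gaps. It names no attendance-to-survey check and gives no error rate. An ellipsis follows the rule in the SAP text available here, so the absence of a further check can be stated only for the text as supplied.

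**The category figures are the most sensitive ones available.** This also stands. The SAP's lead measure is the mean, which moves much less (step 2). But the categories are prespecified for comparison with targets, and the Protocol's I2 hypothesis is itself a threshold statement.

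**The check barely repairs the loss.** This stands in full (step 5). A reader might infer that matching surveys would correct I1 and I2. It would not. Its value is an observed under-logging rate, and even that comes from one proctored session that may be logged better or worse than the others.

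**The correction only adds attendance.** This is true. Sessions logged in error would raise dosage, and the match does not detect them. For that reason the result under the stated rule must stay in the report.

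**Both surveys might be read as proof of workshop attendance.** The documents do not support that for the entrance survey, because it may be taken at orientation.

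**Conclusion.** The SAP's rule conflicts with its own admission, and omitted entries lower I2. The mean is moderately sensitive: 0.9 to 4.5 percentage points at 1% to 5% loss from a true 90%. The 90% and 100% categories are more sensitive: about 2 to 15 points and 12 to 43 points over the same range under the step 3 model. These sizes rest on assumed loss rates, session counts and independent losses. They show what could happen, not that logging here is poor.

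Two stronger readings go too far. One is that fidelity (I1) is seriously distorted: under independent losses the any-workshop percentage hardly moves, although it would if whole records were lost, and the surveys cannot speak to service contacts, referrals or employment supports. The other is that the outcome findings are at risk: the R1 to R3 sample is defined by consent and two completed surveys, so the attendance rule does not enter those tests. This is a cheap improvement to a descriptive implementation result.

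**What to change.** Before computing I2:

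1. Match each exit survey to the last-session attendance record by nFORM client ID and, where available, survey date. Set aside surveys taken outside a session.
2. Where presence is confirmed and attendance is blank, correct the record.
3. Report the mismatch rate (blanks divided by exit surveys confirmed as taken in session) with its denominator, as an estimate of under-logging.
4. Report the I2 mean and attendance categories under the stated rule, and again over a sensitivity range built on that rate. For the mean, divide the recorded value by (1 − e); for example, 85.5%/0.95 = 90%. For the categories, re-tabulate over the same values of e.
5. State the limits: about one session per father is corrected directly; the last session may not represent the rest; service contacts, referrals and employment supports are not checked; attendance logged in error is not detected.

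The cost is one match within nFORM and a few added table columns, with no new data collection. One thing needs confirming first: the Protocol lists the client ID for linking but does not say whether the export carries the survey date or setting. If it does not, the match shows less and the report should say so.
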